## CHAPTER 8 SAMPLE SIZE AND STATISTICAL ANALYSIS

926  
927  
928  
929  
930  
  
931  
932  
933  
934  
935  
936  
937  
938  
939  
940  
941  
942  
943  
944  
945  
946  
947  
948  
949  
950  
951  
952  
953  
954  
955  
956  
957  
958  
959  
960  
961  
962  
963  
964  
965  
966  
967  
968  
969  
970  
971  
972  
973

The estimation of sample size and the statistical analysis plan are summarized below and detailed in separate documents. The analysis plan synopsis in this chapter contains the framework of the anticipated final analysis plan, which will supersede this section when it is finalized.

### 8.1 Sample Size Estimation

The sample size estimate was computed based on a Fisher's exact test comparing proportions of patients in each treatment group with 20/25 or better visual acuity at the 17-week masked exam. Patients meeting this criterion will be considered a treatment success. Based on data from ATSS3 patients meeting eligibility criteria for the ATSS-VT study, it is estimated that 30% of patients in the control vision therapy group will have 20/25 or better visual acuity at the 17-week masked exam. To detect an absolute increase of 20% in the active vision therapy group to an outcome proportion of 50% with type I error of 5% (one-sided) and power of 90%, a total of 222 patients is needed. Patients who drop out of the study prior to completion of the 17 week masked exam will be counted as treatment failures in the primary outcome analysis; hence, no adjustment to the sample size has been made for dropouts.

A one-sided alpha is used as there is interest in testing only whether the outcome proportion for active vision therapy is significantly higher than for controls. If not higher, then there is no reason to use active vision therapy in clinical practice. An absolute increase in outcome proportion of 20% was chosen as the smallest improvement for which clinicians would be willing to use vision therapy in their clinical practice, given the time commitment and extra expense demanded of patients.

Counting dropouts as treatment failures may lower the expected proportion with treatment success in both treatment groups. In this case, the power for the primary outcome comparison is increased to greater than 90%. Adjustment for baseline visual acuity in the primary analysis also would be expected to improve statistical power.

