#### *Observation phase sample size*

Based on the responder rates assumed for the trial sample size calculation, it is expected that  $111 \times 0.30 = 33$  patients from the control group and  $111 \times 0.50 = 56$  patients from the active VT group will be eligible for the observation phase, for a total of 89 patients. However, patients who drop out of the trial prior to completion will not be available for enrollment into the observation phase, and additional patients may drop out during the observation phase. Assuming that 20% of observation phase-eligible patients drop out at any stage of the trial, about 70 patients will have complete observation phase data; of these, 44 will be from the active VT group and 26 from the control group.

974 The primary goal of this phase will be to estimate the proportion of patients with recurrence of  
975 amblyopia (as defined in protocol section 5.1.4) during the 1 year observation phase. Based on  
976 data from ATS3, the expected proportion with recurrence in the control group is 7%. If the  
977 recurrence in the VT study is similar, the expected width of the 95% confidence interval on the  
978 recurrence proportion will be  $\pm 8\%$  for the active VT group,  $\pm 11\%$  for the control group, and  
979  $\pm 7\%$  for both groups combined.

980

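### Section 8.1 says counting dropouts as failures raises power above 90%; with equal dropout it lowers power, to about 85% at 10% dropout and 78% at 20%

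*Protocol*

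**What the plan says.** Protocol section 8.1 gives the basis for the sample size: "The sample size estimate was computed based on a Fisher's exact test comparing proportions of patients in each treatment group". For the control group, "it is estimated that 30% of patients in the control vision therapy group will have 20/25 or better visual acuity". The target is set this way: "To detect an absolute increase of 20% in the active vision therapy group to an outcome proportion of 50" percent, with "type I error of 5% (one-sided) and power of 90" percent, for which "a total of 222 patients is needed".

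Patients who leave before the 17-week masked exam are scored as failures, and the section concludes: "hence, no adjustment to the sample size has been made for dropouts". Its last paragraph accepts that this scoring may lower the expected success proportion in both groups and continues: "In this case, the power for the primary outcome comparison is increased to greater than 90" percent. It then names adjustment for baseline acuity as a further expected source of power, without a figure.

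Section 8.2 confirms the rule: the primary analysis is by intent to treat, using logistic regression adjusted for baseline acuity, with dropouts as failures.

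No 17-week dropout rate is given. Two passages bear on it. Section 7.1 expects withdrawal to be very infrequent. The observation-phase sample size in section 8.1 uses a figure that spans the whole study: "Assuming that 20% of observation phase-eligible patients drop out at any stage of the trial, about 70 patients" then remain with complete data.

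**The concern.** Two proportions with a fixed difference are easier to separate when both lie further below 50%, because the binomial variance is smaller. The power sentence appears to rest on that fact. Scoring dropouts as failures does not keep the difference fixed, however. It multiplies each arm's success rate by the fraction who stay, so the difference shrinks as well.

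Two things depend on the sentence. It supports the decision to make no allowance for dropout, and it tells readers that 90% is a lower bound on power. If the direction is wrong, a null result would be read as coming from a trial with at least 90% power when the actual power was lower. Those deciding whether to go on from the feasibility phase to the full 222 would have the same mistaken figure before them.

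**Working it through.** **Inputs from the protocol.** Control success 30%, active success 50%, one-sided alpha 5%, power 90%, Fisher's exact test and total 222 (all section 8.1); 1:1 allocation (section 3.1), so 111 per arm; dropouts counted as failures with all randomized patients in the denominator (sections 8.1 and 8.2).

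**Assumed.** A dropout fraction d that is the same in both arms and unrelated to outcome, shown from 0 to 20%.

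**Step 1: reproduce the plan's figure.** The continuity-corrected formula for two proportions (0.30 vs 0.50, one-sided 5%, 90% power) gives 111 per arm, or 222. Full enumeration of the one-sided Fisher test at 111 per arm gives 90.0% power. The stated sample size therefore reproduces with no dropout and has almost no slack.

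**Step 2: apply the failure rule.** The rates in the primary analysis become

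- control: 0.30(1−d)
- active: 0.50(1−d)
- difference: 0.50(1−d) − 0.30(1−d) = 0.20(1−d)

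**Step 3: compare the loss in difference with the gain in variance at d = 10%.**

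- The rates are 27% and 45%, and the difference falls from 20 to 18 points, a loss of 10%.
- The variance sum p(1−p) over the two arms falls from 0.21 + 0.25 = 0.4600 to 0.1971 + 0.2475 = 0.4446.
- The standard error is therefore multiplied by √(0.4446/0.4600) = 0.983, a reduction of about 1.7%.
- A 10% smaller difference over a 1.7% smaller standard error means less power.

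**Step 4: power with 111 per arm.** Both tests are one-sided at 5% and fully enumerated. The score test is unadjusted and is shown because it is closer to the planned logistic model.

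| d | Rates | Difference (points) | Fisher exact | Score test |
|---|---|---|---|---|
| 0 | 30.0% vs 50.0% | 20.0 | 90.0% | 92.3% |
| 2% | 29.4% vs 49.0% | 19.6 | 89.2% | 91.7% |
| 5% | 28.5% vs 47.5% | 19.0 | 87.9% | 90.6% |
| 10% | 27.0% vs 45.0% | 18.0 | 85.3% | 88.4% |
| 15% | 25.5% vs 42.5% | 17.0 | 82.1% | 85.6% |
| 20% | 24.0% vs 40.0% | 16.0 | 78.5% | 82.4% |

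Power falls at every step under both tests. By the formula in step 1, keeping 90% power would take 242 patients at 5% dropout, 262 at 10% and 312 at 20%.

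**Step 5: find the conditions under which the sentence is true.** If the difference stays at 20 points from the lower base, Fisher power is 90.6% (28.5% vs 48.5%), 91.2% (27% vs 47%) and 92.0% (24% vs 44%). Keeping that gap after the failure rule needs a difference among completers of 20/(1−d) points: 22.2 at 10% dropout and 25 at 20%. Power can also rise with unequal dropout: 10% control and 5% active gives 27% vs 47.5% and 92.3% power. The reverse, 5% control and 10% active, gives 28.5% vs 45% and 78.8%.

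**Step 6: check whether 30% and 50% already include dropouts as failures.** Section 8.1 says the failure rule may lower the expected proportions, so the stated rates come before it. The observation-phase calculation agrees. It takes 111 × 0.30 = 33 and 111 × 0.50 = 56 as eligible responders, and only then removes patients who drop out, including those lost before the trial exam.

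**The case against.** The strongest defence is that section 8.1 sets its target as an absolute increase of 20 points in the outcome proportion, called the smallest improvement that would lead clinicians to use the therapy. The outcome proportion in the primary analysis counts dropouts as failures. If 20 points is meant on that scale, a lower base rate does raise power, as step 5 shows, and this is probably what the authors had in mind. It remains an unstated assumption. Section 8.1 reaches 50% by adding 20 points to 30%, then says dropout may lower both proportions, without saying that the gap is preserved or that completers are expected to differ by more than 20 points.

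Three further points bear on size:

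- **Dropout rates.** The 10% and 20% are not the protocol's 17-week rates. Its 20% covers every stage, including 12 months of observation, and section 7.1 expects few withdrawals. At 2% to 5% dropout the Fisher loss is only about 1 to 2 points. Against that, the feasibility section of 1.3 lists adherence to weekly visits as a concern, so low dropout is not assured.
- **Planned test.** The unadjusted score test stays at or above 90% up to about 6% dropout, and baseline adjustment may add something. That power comes from the choice of test and the covariate; dropout still reduces it.
- **Sample-size inflation.** Every randomized patient stays in the denominator, so the usual inflation for lost observations does not apply. This is correct, but the smaller effect still needs an allowance or a statement.

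Section 8 also refers to separate documents for detail. That does not excuse a statement of the wrong direction in the protocol itself.

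**Conclusion.** The statement is wrong as written. When dropout is equal in both arms and unrelated to outcome, scoring dropouts as failures lowers power at every rate checked. On the protocol's own sizing test the loss from 90.0% is about 2 points at 5% dropout, 5 at 10%, 8 at 15% and 11.5 at 20%. On the score test the fall is from 92.3% to 88.4% at 10% and 82.4% at 20%.

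The direction is firm under those conditions. The size depends on a 17-week dropout rate that the protocol does not give. The loss is small if withdrawals are as rare as section 7.1 expects, and material at 10% or more. A rise above 90% needs either a 20-point gap that survives the failure rule or suitably higher dropout in the control arm, and section 8.1 states neither. The sample size of 222 is correct for 30% versus 50% without dropout.

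**What to change.** In section 8.1, delete the sentence claiming increased power and the reasoning that the failure rule makes an allowance for dropout unnecessary. Replace them with one of the following:

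1. The power of 222 patients over a range of assumed dropout, equal in both arms: about 88%, 85%, 82% and 78% at 5%, 10%, 15% and 20% (Fisher's exact test, one-sided 5%).
2. A statement that 30% and 50% are the expected rates after dropouts have been counted as failures. The 90% then stands, and the observation-phase calculation must be brought into line, because it now removes trial dropouts from those same rates.

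The sentence on baseline adjustment can stay as a separate expectation. It should not be offered as making up for dropout unless a figure is given.

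The cost is a text change and, under the first option, a less favourable stated power. No extra patients are needed, and the endpoint, the analysis and the type I error do not change.

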#### *Feasibility phase sample size*

A feasibility phase sample size of 45 patients is judged sufficient to meet feasibility phase goals as specified in section 1.3. It is anticipated that there will be 7 clinical sites with each site expected to enroll 6-7 patients. No site will be permitted to enroll more than 10 patients. The sites participating in the feasibility phase will be selected on the basis of ability to enroll children in the desired age range and will provide an upper limit for likely monthly recruitment per site in the full-scale study.

#### *Observation phase sample size*

Based on the responder rates assumed for the trial sample size calculation, it is expected that  $111 \times 0.30 = 33$  patients from the control group and  $111 \times 0.50 = 56$  patients from the active VT group will be eligible for the observation phase, for a total of 89 patients. However, patients who drop out of the trial prior to completion will not be available for enrollment into the observation phase, and additional patients may drop out during the observation phase. Assuming that 20% of observation phase-eligible patients drop out at any stage of the trial, about 70 patients will have complete observation phase data; of these, 44 will be from the active VT group and 26 from the control group.

974 The primary goal of this phase will be to estimate the proportion of patients with recurrence of  
975 amblyopia (as defined in protocol section 5.1.4) during the 1 year observation phase. Based on  
976 data from ATS3, the expected proportion with recurrence in the control group is 7%. If the  
977 recurrence in the VT study is similar, the expected width of the 95% confidence interval on the  
978 recurrence proportion will be  $\pm 8\%$  for the active VT group,  $\pm 11\%$  for the control group, and  
979  $\pm 7\%$  for both groups combined.

980

#### 981 *Sample size for Active VT phase for non-responding controls*

982 Patients in the control group who have not met the criterion for treatment success at the 17 week  
983 masked exam will be offered a 16 week course of active VT treatment free of charge. After the  
984 16 weeks of treatment, these patients will have an outcome exam that mirrors the 17-week RCT  
985 outcome exam. The goal of this phase is to obtain an estimate of the proportion of control  
986 patients who meet criteria for treatment success at this second outcome exam following a course  
987 of active VT treatment.

988

989 It is estimated that about  $\frac{1}{2}$  of patients who are eligible for this phase of the study will elect to  
990 participate; this corresponds to 40 patients. With this sample size, the expected  $\frac{1}{2}$  width of the  
991 95% confidence interval on the proportion of treatment success is approximately  $\pm 10\%$ ,  
992 assuming an underlying success proportion of 10%.

## 993 **8.2 Primary Outcome Analysis**

994

995 The primary analysis will consist of a comparison of proportions of patients in the two treatment  
996 groups who have 20/25 or better visual acuity at the 17-week outcome exam, with adjustment for  
997 baseline visual acuity, using logistic regression. The primary analysis will follow the ‘intent-to-  
998 treat’ principle in which patients are analyzed according to randomized treatment assignment,  
999 regardless of whether the treatment was actually received or completed. Dropouts will be  
1000 counted as treatment failures in the primary analysis.

1001

1002 A secondary analysis that counts study dropouts as treatment successes will be performed. The  
1003 true treatment effect must be bracketed within the estimated treatment difference obtained in the  
1004 primary analysis and this secondary analysis. If these are within 10% of each other using the  
1005 absolute difference, the primary analysis will be considered the definitive analysis. Otherwise,  
1006 both estimates will be included in the publication of study results along with a discussion of the  
1007 implications for study conclusions and patient management.

1008

1009 A secondary analysis that estimates the treatment difference based on study completers only also  
1010 will be performed.

1011

1012 The treatment effect in subgroups based on baseline factors will be assessed in preplanned  
1013 secondary analyses of the primary outcome. The subgroups of interest will be those based on  
1014 baseline amblyopic eye visual acuity, age, baseline stereoacuity, prior treatment, practice type  
1015 (ophthalmology or optometry), and treatment compliance (excellent/good or fair/poor). In  
1016 accordance with NIH guidelines, estimates of treatment effect by gender and race/ethnicity also  
1017 will be computed.

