**508 3.1 Randomization Groups**

509

510 Each patient will be randomly assigned to one of two treatment groups in a 1:1 ratio:

- 511 1. Two (2) hours of daily patching combined with 30 minutes of daily near activities at  
512 home, 30 minutes of daily at-home active vision therapy, and a weekly 45 minute in-  
513 office active vision therapy session.
- 514 2. Two (2) hours of daily patching combined with 30 minutes of daily near activities at  
515 home, 30 minutes of daily at-home control vision therapy, and a weekly 45 minute in-  
516 office control vision therapy session.

517

518 Spectacle wear will be continued if prescribed. Patients wearing contact lenses must be switched  
519 to spectacles prior to enrollment for the duration of the study.

520

521 Weekly Office Visits: Each patient randomized into the study will be seen on a weekly basis for  
522 administration of treatment for 16 weeks. At each office visit, the patient will be queried  
523 regarding diplopia and visual acuity in each eye will be measured using the eETDRS protocol.  
524 Each group will receive 45 minutes of vision therapy activities dependent upon their group  
525 assignment.

526

527 Daily patching and at-home vision therapy will be continued through the 17 week masked  
528 examination.

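### Scoring all dropouts as failures and then all as successes does not bracket the treatment effect, so the 10% rule built on it reacts only to a difference in dropout rates between the arms

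*Protocol*

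**What the plan says.** Protocol section 8.2 sets the primary analysis as a baseline-adjusted logistic comparison of the proportions with 20/25 or better at 17 weeks, by randomized arm, with dropouts as failures. Then: "A secondary analysis that counts study dropouts as treatment successes will be performed". It asserts that the "true treatment effect must be bracketed within the estimated treatment difference obtained in the" primary and this secondary analysis, and builds a rule on that: "primary analysis and this secondary analysis. If these are within 10% of each other using the" absolute difference, the primary analysis is taken as definitive. Otherwise both estimates are to be published, with a discussion of what they imply.

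A completers-only analysis is also planned, but the rule does not use it. No analysis scores dropouts differently by arm. Section 8.1 makes no dropout allowance in the sample size, on the ground that dropouts count as failures.

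**The concern.** Two estimates bound an effect only if they are the extremes that the missing outcomes allow. These are not. Moving every dropout from failure to success in both arms shifts both success rates in the same direction, and most or all of the shift cancels in the difference. The extremes arise when active dropouts are scored one way and control dropouts the other.

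This is the protocol's only stated rule for judging whether missing outcomes threaten the primary result. It also decides whether readers must be shown a second estimate and a discussion. A rule that looks only at unequal dropout will pass a trial with heavy but balanced loss.

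**Working it through.** **Inputs from the protocol.** Section 8.1: "it is estimated that 30% of patients in the control vision therapy group will have 20/25 or better visual acuity"; "To detect an absolute increase of 20% in the active vision therapy group to an outcome proportion of 50"%; "type I error of 5% (one-sided) and power of 90%, a total of 222 patients"; "The sample size estimate was computed based on a Fisher's exact test comparing proportions". Section 3.1: 1:1 allocation, so n = 111 per arm.

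**Assumption.** Dropout by 17 weeks. The protocol gives no rate for the randomized phase. The 20% in section 8.1 concerns patients eligible for the observation phase, at any stage of the trial.

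**The plan's own figure.** The usual two-proportion formula, one-sided 5%, 90% power, 30% vs 50%, gives 101 per arm. With the continuity correction it gives 111, a total of 222, as stated. Exact Fisher power at 111 per arm is 90.0%.

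**The gap between the two planned analyses.** Let sA, sC be observed successes and dA, dC dropouts in the active and control arms.

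- All dropouts fail: F = (sA - sC)/n
- All dropouts succeed: S = (sA + dA - sC - dC)/n
- Gap: S - F = (dA - dC)/n

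The overall amount of dropout does not enter, and neither do the dropouts' real outcomes.

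**The actual bounds.** If dropouts' true success rates are qA and qC, the full-data difference is F + (dA·qA - dC·qC)/n. It must lie between F and S if qA = qC, that is, if treatment makes no difference among dropouts. With qA and qC free between 0 and 1:

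- Lower (active dropouts fail, control dropouts succeed): F - dC/n
- Upper (the reverse): F + dA/n
- Width: (dA + dC)/n, the sum of the dropout rates, not their difference

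These bound the difference in the randomized sample; sampling error comes on top.

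**Equal dropout, 111 per arm, completers succeeding at about 50% vs 30%.**

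| Dropouts per arm | Successes, active vs control | All fail | All succeed | Gap | Bounds (points) |
|---|---|---|---|---|---|
| 5 (4.5%) | 53 vs 32 | 21/111 = 18.9 | (58 - 37)/111 = 18.9 | 0 | 16/111 = 14.4 to 26/111 = 23.4 |
| 11 (9.9%) | 50 vs 30 | 20/111 = 18.0 | (61 - 41)/111 = 18.0 | 0 | 9/111 = 8.1 to 31/111 = 27.9 |
| 22 (19.8%) | 44 vs 27 | 17/111 = 15.3 | (66 - 49)/111 = 15.3 | 0 | -5/111 = -4.5 to 39/111 = 35.1 |

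In every row the supposed bracket is a single point and the rule returns definitive. In the last row the completers-only estimate is 44/89 - 27/89 = 19.1 points, outside that point.

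**When the bounds reach zero.** With completer rates of 50% and 30% and equal dropout fraction d, the lower bound is 0.20(1 - d) - d. It is zero at d = 0.20/1.20, about 17% per arm.

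**A benign case that already fails.** If dropouts resemble completers, the full-data difference is 20 points. At 20% dropout per arm both analyses give 0.80 × 20 = 16 points.

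**Unequal dropout, same completer rates.**

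- 30% active vs 20% control: F = 0.35 - 0.24 = 11 points, S = 21, gap 10, still at the limit. Bounds: 11 - 20 = -9 to 11 + 30 = +41.
- 25% vs 10%: F = 0.375 - 0.27 = 10.5, S = 25.5, gap 15. Here the rule does trigger.

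**Baseline adjustment.** The identity is exact for raw proportions and approximate for the planned logistic model. In a simulated set of 200,000 patients with equal random dropout, the adjusted risk differences (all fail, all succeed) were 0.161 and 0.161 at 20% dropout and 0.119 and 0.118 at 40%, against 0.20 with full data. Adjustment does not rescue the bracket.

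**The case against.** The other side has several fair points.

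- **Dropout may be small.** Section 7.1 expects withdrawals to be very infrequent, and section 8.8 has 17-week retention estimated in the feasibility phase. At 5 or 11 dropouts per arm the lower bound stays clearly positive. The -4.5 needs all 22 active dropouts to fail and all 22 control dropouts to succeed. This stands and limits the practical size of the problem. But a missing-data safeguard is needed precisely when dropout is not small.
- **The rule does react to something real.** Section 1.3 singles out adherence in the control group, and unequal loss would widen the gap. A reader might infer that the rule approves the primary analysis at any dropout rates whatever. The text does not support that: it fails to trigger only while the arms differ by no more than about 10 points.
- **Completers-only results will exist.** True, and they can differ from the primary estimate, but they play no part in the rule.
- **Failure scoring is often conservative.** With equal dropout it overstates the benefit only if control dropouts would have succeeded more often than active dropouts. This supports keeping it as primary; it does not make the bracketing claim true.
- **The rule cannot be blamed for missing outcome-dependent dropout.** Agreed: no analysis of observed outcomes can detect it. The fair criticism is that the rule claims to bound its effect and does not.
- **Chapter 8 says a final analysis plan will supersede it.** That would excuse missing detail. It does not excuse a false statement and a decision rule that rests on it.

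**Conclusion.** The bracketing statement in section 8.2 is wrong as written, and the 10% rule measures only differential dropout. With the arms' dropout rates within 10 points of each other, the primary analysis is labelled definitive regardless of how much is missing. At the assumed levels the range hidden behind a gap of zero is 9 points wide (5 dropouts per arm), 20 (11 per arm) or 40 (22 per arm). At 50% vs 30% among completers, it includes zero from about 17% equal dropout. These dropout levels are assumptions; the algebra is not.

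A reader might go further and infer that the primary result itself is invalid. The protocol does not support that: the endpoint, the scoring of dropouts as failures, the logistic model, alpha and the 222 patients do not depend on the rule. What depends on it is the definitive label and whether the second estimate and a discussion must be published. It should be fixed, but it is not a fatal flaw.

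**What to change.** In section 8.2, and in the analysis plan if it repeats the text:

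1. Keep dropouts as failures in the primary analysis, and keep the completers-only analysis.
2. Delete the bracketing sentence and the 10% rule.
3. Report the two opposite-direction bounds: active dropouts fail with control dropouts succeeding, and the reverse. A tipping-point grid over the dropout success rates in each arm is a useful option.
4. Base any statement of robustness on whether the primary conclusion holds across those bounds. If it does not, publish the range with a discussion.

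The cost is a few sentences and a few lines of code, with no new data, patients or visits. The change should be settled before unmasked results are seen. The one drawback is a less favourable robustness statement when dropout is high.
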